4.2 PHARMACOKINETICS

4.2.1 Available data

Blood samples will be collected for the determination of efgartigimod concentration at the time points indicated in the schedule of assessments (see appendix 9.5). Sampling will be done predose on IMP administration visits (within 2 hours before IMP).

In Part A only, 1 additional PK sample will be collected from all participants on day 10 (±1 day; should be collected at least 2 days after the second IMP dose is administered at week 1).

Following PK samples will be excluded from the descriptive statistics based on time since previous IMP:

- When PK sampling is deviating more than 2 days from scheduled sample visit: i.e., if PK sample is not within last IMP+7 days ± 2 days.
- For the Day 10 visit when PK sampling is deviating more than 1 day from scheduled sample visit: i.e., if PK sample is not within second IMP+2 days ± 1 day.
- When a predose sample is taken after IMP administration.
- When the IMP administration prior to the scheduled PK sample is missed (not applicable for Day 1).

A remark with reason for exclusion of the time point will be added in the appropriate listing.

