- o At BL (week 0 [day 1]) and week 1 (day 8), mg of IMP (efgartigimod PH20 SC or placebo) will be administered via SC injections (Table 6). At weeks 2 through 35, 1000 mg of IMP (efgartigimod PH20 SC or placebo) will be administered via a single SC injection.

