8.1.3. Treatment and Follow-Up Periods

- Each participant should attend each study visit on the designated days (Table 1). There is a permissible visit window of ±2 days during the treatment period and ±3 days during the treatment-free follow-up period.
- Immediate safety concerns should be discussed with the sponsor immediately upon occurrence or awareness to determine if the participant should continue or discontinue IMP. Additionally, an independent unblinded DSMB may review all unblinded safety data on a regular basis as specified in Section 10.1.5.
- Participants who received IMP throughout the entire the 36-week treatment period will complete the EoTP visit assessments (Table 1) at week 36.
- Participants who discontinue IMP early will complete an ETD visit (Table 1), may begin rescue therapy (Section 6.8.3), continue their treatment period visits as scheduled, and then complete the EoTP assessments (Table 1) at week 36.
- Participants who withdraw consent or are permanently discontinued from the study will complete an ESD visit (Table 1); details for the study discontinuation procedures are provided in Section 7.2.
- Participants who complete the EoTP visit and choose not to enroll in the OLE study ARGX-113-2010 will complete the treatment-free follow-up period visits at weeks 39 and 43 (Table 1).

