2.2.4 Analysis visits

For longitudinal responses, all assessments, including unscheduled assessments, will be allocated to analysis windows as defined below. Tables and listings will present the analysis windows, not the case report form (CRF) visits. Allocation of assessments will be done using their relative day (DY, see section 2.2.3). Visit window limits are the mid-point between the scheduled study days for each visit.

Table 2: Analysis visits (for assessments other than disease status)

	•		1.5	
Phase	Analysis window	Target DY	Lower limit DY	Upper limit DY
Screening	Screening ^[2]	-14	-INF	1
Treatment	Baseline	1	-INF	1[1]
	Week 1	8	1[1]	11
	Week 2	15	12	18
	Week 3	22	19	25
	Week 4	29	26	43
	Week 8	57	44	71
	Week 12	85	72	99

Page 26 of 120

SGS		Statistical	Analysis Plan	
ARGX-113-2009		Final and	Interim Analysis	Final 4.0 of 04NOV2024
	Week 16	113	100	127
	Week 20	141	128	155
	Week 24	169	156	176
	Week 26 ^[2]	183	177	190
	Week 28	197	191	211
	Week 32	225	212	239
	Week 36 ^[2]	253	240	End of treatment phase

1

36

35

End of FU phase

FU Week 7

Follow-up [3] FU Week 3

21

49

Table 3: Analysis visits (for disease status assessments)

Phase	Analysis window	Target DY	Lower limit DY	Upper limit DY
Screening	Screening	-14	-INF	1
Treatment	Baseline	1	-INF	1[1]
	Week 1	8	1[1]	11
	Week 2	15	12	18
	Week 3	22	19	25
	Week 4	29	26	32
	Week 5	36	33	39
	Week 6	43	40	46

	Week X ($X = 7 \text{ to } 34$)	X*7+1	X*7-2	X*7+4

	Week 35	246	243	249
	Week 36 ^[2]	253	250	End of treatment phase
Follow-up [2]	FU Week 3	21	1	35
	FU Week 7	49	36	End of FU phase

[figure not shown]
^[1] An assessment on Day 1 will be attributed to Baseline in case it is before the first administration, to Week 1 otherwise.

^[1] An assessment on Day 1 will be attributed to Baseline in case it is before the first administration, to Week 1 otherwise.

^[2] ECG is only captured at screening, W26, W36, ETD and ESD.

^[3] The start date of the follow-up phase will be used as a reference date for the DY calculation.

^[2] The start date of the follow-up phase will be used as a reference date for the DY calculation.

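### SAP 4.2.1: applied as written, the 7 ± 2-day PK exclusion clause empties the week 39 and week 43 rows of the concentration tables and contradicts its own lead-in

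*SAP*

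**What the plan says.** SAP 4.2.1 opens its list of exclusions with "Following PK samples will be excluded from the descriptive statistics based on time since previous IMP". The first bullet has two parts. The lead-in is "When PK sampling is deviating more than 2 days from scheduled sample visit". The numeric clause that explains it is "if PK sample is not within last IMP+7 days ± 2 days". Day 10 has its own clause, "if PK sample is not within second IMP+2 days ± 1 day". A further bullet removes samples preceded by a missed dose and exempts Day 1, but that exemption belongs to that bullet only. No bullet mentions the follow-up visits.

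On the schedule, the protocol SoA footnote on dosing reads "At weeks 2 through 35, 1000 mg of IMP", so week 35 is the last dose. Protocol 8.1.3 says that participants who finish treatment and do not enter the extension study "will complete the treatment-free follow-up period visits at weeks 39 and 43". Protocol 8.1.3 gives the permitted visit window as ± "2 days during the treatment period and ±3 days during the treatment-free follow-up period".

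The protocol SoA and SAP 9.5 both mark PK at baseline, end of treatment, F1, F2, ETD and ESD. Protocol 8.5 allows PK sampling at visits without dosing. SAP Table 2 defines FU Week 3 and FU Week 7 analysis windows, and SAP 4.2.3 plans descriptive statistics by time point together with a listing of individual values.

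**The concern.** The plan sets up follow-up time points for concentration data and then states a numeric rule that no on-schedule follow-up sample can meet. Programmed from the numeric clause, the concentration table would have empty follow-up rows, and the decline after the last dose would not be described in any SAP table. Efgartigimod serum concentration is a secondary endpoint in both parts.

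No other planned table makes up for this. SAP 4.3.3 presents PD results on all available data and repeats them with late samples removed, but PK has no all-data version. The tables of mean concentration by antibody classification in SAP 4.4.3 are also descriptive and state no exemption.

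The bullet also contradicts itself for these visits. Two programmers could produce different tables from it and both claim to have followed the SAP.

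**Working it through.** **Inputs**
- Accepted gap since last IMP: 7 ± 2 days, so 5 to 9 days (SAP 4.2.1).
- Last dose: week 35 (protocol SoA). SAP Table 3 gives the row "Week 35 246 243 249", so the target is day 246.
- Follow-up visits: weeks 39 and 43 (protocol 8.1.3).
- Windows: ±2 days on treatment, ±3 days in follow-up (protocol 8.1.3).

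**Formulas.** Study day = 7 × week + 1. Gap = sample day − last dose day. A sample is kept if 5 ≤ gap ≤ 9.

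**The rule fits the visits it was built for**
- Week 36: day 253 − day 246 = 7 days, the centre of the window. Over all 5 × 5 = 25 combinations of ±2-day windows, the gap runs from 3 to 11 days and 19 are kept.
- Day 10: 10 − 8 = 2 days, the centre of its own window.

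**Follow-up visits**
- Last dose: day 246 ± 2, so days 244 to 248.
- F1: 7 × 39 + 1 = day 274, ±3 gives 271 to 277. Nominal gap 274 − 246 = 28 days; range 271 − 248 = 23 to 277 − 244 = 33 days.
- F2: 7 × 43 + 1 = day 302, ±3 gives 299 to 305. Nominal gap 302 − 246 = 56 days; range 299 − 248 = 51 to 305 − 244 = 61 days.
- Of the 5 × 7 = 35 window combinations at each visit, 0 fall within 5 to 9 days.
- For even the earliest permitted F1 sample (day 271) to qualify, the last dose would have to be on day 271 − 9 = 262 or later. Week 37 is day 260, so this is more than two weeks beyond the end of dosing.

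**Other samples caught by the same clause**
- Baseline: there is no previous dose, so the condition cannot be met.
- Early discontinuation: participants are encouraged to keep attending the mandatory on-site visits. As an illustration, with a last dose at week 20 (day 141) the week 24 sample (day 169) has a gap of 28 days and is dropped. Later samples have longer gaps.

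**The lead-in taken alone.** Judged by distance from the scheduled day (±2 days), follow-up samples on 5 of the 7 permitted days are kept at each of F1 and F2. The numeric clause keeps 0 of 7.

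**The case against.** The strongest reply is that the bullet is about deviation from the scheduled visit, and that the numeric clause only restates this for weekly dosing, where the scheduled visit is 7 days after the previous dose. On that view an F1 or F2 sample taken on its scheduled day deviates by 0 days and stays in. Two features support it. Read literally, the numeric clause would also drop every baseline sample, which can hardly be intended. And SAP Table 2 defines follow-up windows, which suggests that those visits were meant to be tabulated. This is a plausible account of the intent. But the sentence introducing the list bases exclusion on time since dose, and the numeric clause is the part that can be programmed directly, so the text as it stands does not deliver that intent.

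A reader might go further and infer that the follow-up data are never used, that blood is drawn for nothing, or that a secondary endpoint is left unreported. The documents do not support this. Individual concentrations are listed with sampling times, and exclusions carry a reason. Protocol 9.3.3.2 allows a population PK/PD analysis of the PK data, reported separately, though it is optional. F1 and F2 also include safety laboratory, PD and immunogenicity blood samples. The endpoint is serum concentration in general and does not name washout, so the on-treatment summaries still address it. Finally, only participants who do not roll over to the extension study have these visits.

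**Conclusion.** The point stands as a defect of wording with a definite consequence. If the numeric clause is applied as written, all scheduled week 39 and week 43 samples leave the SAP's descriptive concentration tables (gaps of 23 to 33 and 51 to 61 days against an allowed 5 to 9). So do baseline samples and samples more than 9 days after early discontinuation. The same bullet's lead-in would keep most of the follow-up samples, so the SAP has to be reconciled with itself.

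This assumes dosing through week 35 and visits within the protocol windows; stopping IMP earlier only lengthens the gaps. The documents do not say how many participants decline roll-over, so the loss can be given as a proportion (all such samples) but not as a count. The importance is low: a descriptive PK summary is affected, and no efficacy inference depends on it.

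**What to change.** Amend SAP 4.2.1 before database lock as follows:
- Apply the 7 ± 2-day rule only to on-treatment predose samples after the first dose, plus the week 36 end-of-treatment sample in participants still on IMP. Week 36 must be named separately because no dose is given at that visit.
- Exempt baseline from the rule.
- Include F1 and F2 samples taken within the protocol's ±3-day visit window.
- Summarise off-IMP samples, both from follow-up and after early discontinuation, separately by time since last dose, so that they do not mix with trough values at the same nominal visit.
- State that the missed-dose exclusion does not apply once IMP has been permanently stopped; otherwise it could be read as removing the same samples.

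The cost is a few lines of SAP text and a programming condition. No new data are needed, and no other analysis changes.

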8.5. Pharmacokinetics

Blood samples for PK analysis will be collected from each participant as described in the SoA (Table 1). Samples will be collected predose on IMP administration visits (within ≤2 hours before IMP administration) and any time if no IMP is administered. During unscheduled visits, blood samples for PK will be collected only if IMP is administered.

In part A only, 1 additional PK sample will be collected from at least 28 participants on day 10 (±1 day; should be collected at least 2 days after the second IMP dose is administered at week 1).

Efgartigimod serum concentrations will be determined using a validated assay.

The actual date and time of collection of each blood sample will be recorded in the requisition form. If no sample is taken, the reason will be recorded in the relevant section of the eCRF.

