Specialty laboratory tests (Section 8.3.6.1)		X							X													
Pharmacokinetics (Section 8.5)		X	X	Xm	X		X	X	x	X	X	X	X	X	X		X	X	X	X	X	X
Immunogenicity (Section 8.9)	X	X			X		X	X	X	X	X	X	X	X	X		X	X	X	X	X	X
Pharmacodynamics (total IgG serum levels; anti-BP180 and anti-BP230 antibodies; serum levels) (Section 8.6)	X	x	X		X		X	X	X	X	x	X	X	x	х		х	X	X	X	X	х
Substudy (selected sites): historical protective antibody titers (serum) (Section 8.3.6.2)		x					X															
Substudy (selected sites): vaccination antibody fiters (serum) (Section 8.3.6.2)			Bef	ore vac	cinat	ion;	first					its at -		eks,	+12 w	eeks, and	+24		(x)		(x)	

Study Period	Screening Period ^a								Tı	eatme	nt Per	iod ^b						THE PROPERTY.	ow-up	0	ther Visi	ts
Visit Type	SCR	BL					M	andat	ory O	n-site	Visits					Other Weekly Visits	EoTP	Fl	F2	ETDd	ESD*	UNSf
Visit Week		0	1	(D10)	2	3	4	8	12	16	20	24	26	28	32	-	36	39	43	ETD	ESD	
Visit Day	-14 to -1	1	8	10	15	22	29	57	85	113	141	169	183	197	225		253					
Visit Window (±days)	+7	-	±2	±1	±2	±2	±2	±2	±2	±2	±2	±2	±2	±2	±2	±2	±2	±3	±3	-	-2	-
Substudy (selected sites): vaccination cellular responses (PBMCs) (Section 8.3.6.2)			Before vaccination; first available on-site visits at +12 weeks and +24 weeks postvaccination																(x)		(x)	
IGA-BP (Section 8.2.1.2)	X	x	X		x	x	X	X	X	x	x	x	x	x	x		x	x	X	X	X	X
BPDAI (Section 8.2.1.3)	X	X	X		X	X	X	X	X	X	X	X	X	X	X		X	X	X	X	X	X
Itch NRS (Section 8.2.1.4)		X	X		X	X	X	X	X	X	X	X	X	x	X		X	X	X	X	X	X
BP disease status ^a		X	X		X	X	X	X	X	X	X	X	X	X	X	X	X	X	X	X	X	X
Concurrent OCS dose monitoring®		X	X		X	X	X	X	X	X	X	X	X	X	X	X	X	X	X	X	X	X
Investigator telephone calls ^p																ΧÞ						
Substudy (selected sites): photography of BP lesions (Section 8.10)		The state of the s		sponsor relapse o		Pho	tos m	ay al	so be		at inte						BL an Phote	d when	CDA also b	s that pho CR, and taken at vestigato	relapse interme	occur. diate
GTI (including C-GTI & GTI-SL)		X							X				X				X			X	X	
AEs	X	X	X	X	X	X	X	X	X	X	X	X	X	X	X	X	X	X	X	X	X	X

ARGX-113-2009 Final and Interim Analysis Final 4.0 of 04NOV2024

Study Period	Screening Period ^a								Ti	eatme	nt Per	iod ^b						The state of the s	w-up iod ^c	0	ther Visi	ts
Visit Type	SCR	BL					M	ndat	ory O	n-site	Visits	É				Other Weekly Visits	EoTP	F1	F2	ETDd	ESD*	UNS
Visit Week		0	1	(D16)	2	3	4	8	12	16	20	24	26	28	32	-	36	39	43	ETD	ESD	
Visit Day	-14 to -1	1	8	10	15	22	29	57	85	113	141	169	183	197	225		253					

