- Follow-up visits are only applicable for participants who choose not to roll over to the OLE study ARGX-113-2010. Additional details are provided in Section 8.1.3.
- The ETD visit must be performed when IMP is discontinued before the EoTP visit; the study site should make every effort to perform this visit within 7 days of the participant's last IMP dose. Participants will remain in the study (provided that they have not withdrawn consent) and will continue to participate in study visits as scheduled, only without IMP administration. Rescue therapy may be initiated at this visit. Additional details are provided in Section 7.1.

- The ESD visit must be performed when the participant either withdraws consent or is permanently discontinued from the study (refer to Section see Section 7.2 for examples of study discontinuation criteria). The study site must make every effort to perform this visit within 7 days of the participant's last IMP dose.
- An unscheduled visit should be performed if the participant has (or suspects they have) new BP lesions, has new AEs, or has other issues requiring site staff intervention.
- 8 No study-related activities can be performed before the participant has provided signed informed consent.
- h Histopathology/DIF are performed only if positive test results are not available as part of the participant's medical history.
- All vaccinations received prior to the study should be recorded as part of the participant's prior medication history, while all vaccinations received during the study should be recorded as concomitant medications.
- WOCBP must have a negative serum pregnancy test and must be performed in WOCBP. Alternatively, postmenopausal female participants must have a serum FSH test to confirm postmenopausal status.
- k Urine pregnancy tests will be performed at the specified visits for WOCBP only.
- In addition to the standard clinical chemistry and hematology parameters (Section 10.2), the screening assessment also includes INR and aPTT.
- "The day 10 PK blood sample will only be collected during part A of the study. The sample should be collected no earlier than day 9, and no later than day 11.
- BP disease assessment (Section 8.2.1.1) must be performed according to the definitions presented in Section 4.1.3.

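### The Day 10 PK exclusion window in SAP 4.2.1 keeps samples taken one day after the second dose, below the collection rule's two-day minimum, and matches the calendar window only for a day 8 dose

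*SAP*

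**What the plan says.** **Collection.** SAP 4.2.1 places an additional Part A sample on day 10, give or take one day, and says it "should be collected at least 2 days after the second IMP dose is administered at week 1". Protocol 8.5 carries the same condition. The schedule footnote in SAP 9.5 restates the calendar limits: "The sample should be collected no earlier than day 9, and no later than day 11". The documents differ on who is sampled. In protocol 8.5, "1 additional PK sample will be collected from at least 28 participants on day 10", whereas SAP 4.2.1 has every Part A participant sampled.

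**Exclusion.** SAP 4.2.1 also lists which samples are left out of the descriptive statistics. Routine samples are dropped "if PK sample is not within last IMP+7 days ± 2 days". The Day 10 rule is first put as a departure of more than one day from the planned visit. It is then restated, as though the two were the same, as a sample being dropped "if PK sample is not within second IMP+2 days ± 1 day".

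**Dose timing.** The second dose is due at week 1, with day 8 as its target. Protocol 8.1.3 says: "There is a permissible visit window of ±2 days during the treatment period". The protocol's schedule of activities also shows ±2 days for the week 1 visit.

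**Use.** The version 3.0 entry in protocol Appendix 15 gives the sample's purpose as describing the expected peak concentration after the second administration. SAP 4.2.3 summarises concentrations by time point and lists individual values with actual sampling times relative to dosing.

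**The concern.** For routine samples, seven days is a target with no minimum attached, so a symmetric tolerance around it is natural. For Day 10, two days is both the centre of the window and the stated minimum, so a symmetric tolerance of one day must let in samples below that minimum.

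The restatement adds a second difficulty. A window counted from the dose and a window counted from the planned visit are different rules unless the dose was on its target day. A programmer who follows the first half of the sentence and one who follows the second would select different samples whenever the week 1 dose is off day 8.

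The stake is one table. Samples at dosing visits are pre-dose, so Day 10 is the only scheduled time point meant to lie near the peak. A summary that mixes samples taken one, two and three days after the dose is harder to read as a near-peak value.

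**Working it through.** **Inputs**
- Permitted second-dose days: 8 ± 2, so days 6 to 10 (protocol 1.3 and 8.1.3).
- Permitted sample days: 10 ± 1, so days 9 to 11 (protocol 8.5; SAP 4.2.1 and 9.5).
- Collection minimum: gap of at least 2 days, where gap = sample day − dose day (SAP 4.2.1; protocol 8.5).
- SAP inclusion window: gap of 2 ± 1, so 1 to 3 days (SAP 4.2.1).

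Gaps are counted in whole calendar days; neither document states the unit.

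**Step 1: reproduce the plan's equivalence.** With the second dose on day *d*, the dose-based window covers days *d* + 1 to *d* + 3.

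| Second dose on day | Dose-based window | Calendar window |
|---|---|---|
| 6 | 7 to 9 | 9 to 11 |
| 7 | 8 to 10 | 9 to 11 |
| 8 | 9 to 11 | 9 to 11 |
| 9 | 10 to 12 | 9 to 11 |
| 10 | 11 to 13 | 9 to 11 |

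The two agree on day 8 and on no other permitted day.

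**Step 2: enumerate the pairs.** There are 5 × 3 = 15 combinations. In three of them (dose 9/sample 9, 10/9 and 10/10) the sample day is not after the dose day, which leaves 12. Each cell gives the gap, whether it meets the two-day minimum, and what the SAP rule does.

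| Dose day | Sample day 9 | Sample day 10 | Sample day 11 |
|---|---|---|---|
| 6 | 3, meets, kept | 4, meets, dropped | 5, meets, dropped |
| 7 | 2, meets, kept | 3, meets, kept | 4, meets, dropped |
| 8 | 1, below, kept | 2, meets, kept | 3, meets, kept |
| 9 | – | 1, below, kept | 2, meets, kept |
| 10 | – | – | 1, below, kept |

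**Step 3: count.**
- Pairs meeting the minimum: 3 + 3 + 2 + 1 + 0 = 9.
- Pairs kept by the SAP: 1 + 2 + 3 + 2 + 1 = 9.
- Kept although below the minimum: 8/9, 9/10 and 10/11, so 3 of the 9 kept.
- Meeting the minimum but dropped: 6/10, 6/11 and 7/11 (gaps 4, 5 and 4), so 3 of 9.

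The first mismatch needs no departure from the dosing schedule: dose on day 8, sample on day 9. The second arises only after a dose on day 6 or 7. After a dose on day 10, no permitted sample day meets the minimum.

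**Step 4: alternative windows.**
- Gaps of 2 to 3 days: 6 pairs kept, none below the minimum; the three pairs with gaps of 4 to 5 days fall outside.
- Gaps of 2 to 5 days: all 9 compliant pairs kept, none below the minimum, but the summary then spans a wider range of times since dose.

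**Step 5: size of the table.** With 28 sampled and an even split, 28 / 2 = 14 are on efgartigimod; with 40, 40 / 2 = 20. One sample is then 1/14 ≈ 7% to 1/20 = 5% of the summary.

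**The case against.** The strongest reply is that the conflict begins in the collection instruction. It is worded as a recommendation, and its own one-day tolerance allows day 9, which is one day after an on-schedule day 8 dose. On this view the exclusion rule merely reproduces the calendar window for a participant dosed on time. The exclusions are also introduced as depending on time since the previous dose, so the anchor is largely right already. Excluded time points carry a reason in the listing and actual sampling times are listed, so no data are lost and anyone can regroup them.

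All of this stands as a limit on importance. It does not remove the mismatch: the planned table would still include samples earlier than the same section advises, and the sentence still offers two definitions that can disagree.

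Three stronger readings are tempting, and the documents do not support them.

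- *That Day 10 is the only concentration summary after loading.* PK is also sampled pre-dose at week 2, after both initial doses, and summarised. Day 10 is the only near-peak one.
- *That the rule wrongly discards compliant samples.* Those it drops are four or five days after an early dose. Leaving them out of a near-peak summary fits the sample's stated purpose; what is missing is a plan to show them elsewhere.
- *That a third of the retained samples will be too early.* The counts are of possible pairs. The documents give no distribution of actual dosing days, so no frequency can be derived.

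**Conclusion.** The point holds as an internal inconsistency in SAP 4.2.1. The inclusion window starts one day below the collection minimum, and its stated equivalence with the visit window is true only for a second dose on day 8. Three of the nine retained day pairs are affected, each with a gap of one day, and one of them occurs with the dose exactly on schedule.

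The consequence is small: one descriptive Part A time point with about 14 to 20 efgartigimod participants, each sample weighing 5 to 7%. That range assumes 28 to 40 participants sampled and an even split between arms. The pair counts rest on whole calendar days and on the full permitted windows being used. No efficacy or alpha-controlled result depends on the rule. The change is worth making because it is cheap and settles which samples enter the only near-peak table.

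**What to change.** In SAP 4.2.1:

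1. Define the Day 10 rule solely by calendar days since the actual second dose, and state the unit.
2. Include samples taken 2 to 3 calendar days after that dose. Do not use a strict 48-hour limit, which would remove an on-schedule day 10 sample drawn earlier in the day than the day 8 dose was given.
3. Delete the restatement in terms of the scheduled visit.
4. Show the remaining samples separately by actual time since dose. These are the one-day samples and the compliant four- to five-day samples after an early dose.

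The same paragraph should also be brought into line with protocol 8.5 on how many participants are sampled.

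The cost is a few lines of SAP text. Injection times and sample dates and times are already recorded (protocol 6.4 and 8.5). The one drawback is that a few one-day samples may leave an already small table; they remain visible in the separate display and in the listing.
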